6.4.2 Toxicity

Toxicities will be graded and reported according to the NCI-CTCAE version 4.03 ([Appendix E](#)). This document can also be downloaded from the Cancer Therapy Evaluation Program (CTEP) home page

http://ctep.cancer.gov/protocolDevelopment/electronic_applications/ctc.htm#ctc_50.

6.4.3 Data Monitoring Committee (DMC)

No DMC will be formed for this trial. Safety will be evaluated on an ongoing basis.

6.5 Concomitant Medication

Throughout the trial, Investigators may prescribe any concomitant medications or treatments deemed necessary to provide adequate supportive care except for the following:

- Use of anti-cancer therapies (eg, chemotherapy, investigational agent) other than those specified in this protocol are not allowed. Palliative radiation is permitted.
- Immunomodulatory agents including but not limited to anti-CTLA4, anti-PD1, anti-PD-L1, sipuleucel-T, cyclosporine, and tacrolimus.
- Coumadin
- Patients on coumadin should be changed to SQ administered low-molecular weight heparin (LMWH) or oral Factor II or Xa inhibitors with a half-life of less than 24 hours.

- Factor II or Xa inhibitor with a half-life of greater than 24 hours.
- High dose steroids (eg, dexamethasone >10 mg/day for more than 14 sequential days).

6.6 Surgery During Trial Period

Patients should not schedule any elective surgeries during their participation in the trial, through 7 days after the last administration of AM0010 or pembrolizumab. If a patient undergoes any unexpected surgery during the course of the trial, that patient must discontinue trial treatment immediately, and Lilly or designee should be notified as soon as possible.

7.0 TRIAL ASSESSMENTS AND PROCEDURES

7.1 General Trial Procedures

Both trial Arm 1 and Arm 2 will follow the same schedule of assessment, unless otherwise noted.

A signed and dated IRB-approved ICF must be obtained before performing any trial-specific screening procedures that is not part of standard medical practice. All screening tests and assessments must be performed within 21 days of trial day 1, unless noted below.

During the trial, every effort should be made to keep the SOA on time for each patient ([Appendix A](#)). All visits should be performed on the visit specified ± 3 days, unless otherwise noted.

Patients will continue to receive trial treatment until they experience progressive disease, unacceptable toxicity, require subsequent anticancer therapy, withdraw consent, or their physician feels it is no longer in their best interest to continue on treatment.

Tumor assessment will be performed for all randomized patients every 9 weeks (± 7 days) during the study treatment and during the first year from discontinuation of the study treatment, every 12 weeks (± 7 days) during the second year, and every 16 weeks (± 7 days) thereafter. Tumor assessment will be repeated until disease progression, death, or receipt of new anti-cancer therapy, or until study completion, whichever is first, whether or not study treatment was administered.

Scans will include head and CAPs and will be sent be to the central imaging vendor for archiving and possible assessment at a later date and possible archiving at a later date. If clinical progression is suspected, all relevant clinical documentation is to be submitted to the central imaging vendor for archiving.

Tumor assessment of all sites of disease will follow RECIST v.1.1 ([Appendix B](#)): CT (or MRI if allergic to contrast). The same radiographic procedure used to define measurable lesions must be used throughout the study for each patient. Assessment should be obtained regardless of cycle number and regardless of any dose withhold until tumor progression. Patients with clinical progression must obtain an unscheduled scan to document disease status per RECIST v1.1. Patients with suspected radiographic pseudoprogression, in the absence of clinical deterioration should remain on trial treatments and be rescanned at 4 weeks or later. If progression is confirmed on follow-up scan per RECIST v1.1, then discontinue study treatments and follow study procedures for end of treatment and follow-ups. At the time of disease progression, patients randomized to trial Arm 2 may crossover to Arm 1 to receive AM0010 and pembrolizumab.

All randomized patients will be followed for OS every 9 weeks (± 7 days) during the first year from the 90-day follow-up visit, every 12 weeks (± 7 days) during the second year, and every 16 weeks (± 7 days) thereafter. The survival follow-up will be conducted until death or study completion, whichever is first, whether or not trial drug was administered. For patients

who were randomized, but withdraw consent, survival (date of death) will be obtained by use of publicly available information.

Safety assessment will follow the guidelines provided in NCI-CTCAE v4.03 ([Appendix E](#)).

7.2 Overview

The trial consists of the following procedures:

(1) **Screening:** The screening period must occur within 21 days prior to dosing, unless otherwise stated. The screening visit may be counted as baseline (Day 1) if completed within 72 hours prior to dosing.

(2) **Treatment:** Patient will be randomized to either:

- Trial Arm 1: AM0010 self-administered as a SQ injection QD (≤ 80 kg body weight = 0.8 mg or >80 kg body weight = 1.6 mg). Pembrolizumab will be administered as intravenous (IV) infusion on Day 1 of a 21-day cycle (200 mg over approximately 30 minutes)

OR

- Trial Arm 2: Pembrolizumab will be administered as an IV infusion on Day 1 of a 21-day cycle (200 mg over approximately 30 minutes)

(3) **Clinical and Laboratory Assessments:**

Complete history, physical examination (Site/Organ System Status [includes: General appearance, skin, H/E/E/N/T – Thyroid, Pulmonary, Cardiovascular, Gastrointestinal, Musculoskeletal/ Extremities, Genitourinary/Breast, Lymph Nodes, Neurological and Psychiatric]), ECOG performance status, height (screening only), weight, vital signs, and documentation of concomitant medications.

Laboratory studies: see Section [7.11](#).

(4) **Continued Treatment:**

At the time of disease progression (as assessed by the Investigator), patients randomized to trial Arm 2 may crossover to Arm 1 receive AM0010 and pembrolizumab.

(5) **End of Treatment:** Patients will return to the trial site 28 days (± 7 days) after the last dose of trial drug for end of treatment assessments.

(6) **Follow-Up Period:**

During the extended safety observation period, all randomized patients will be followed for safety 60 and 90 days (± 7 days) after the last dose of study treatment and monitored according to the SOA ([Appendix A](#)).

During the long-term follow-up period, all randomized patients who discontinue trial treatment before disease progression or patients randomized but not treated will be followed for OS every 9 weeks (± 7 days) during the first year from the 90-day follow-up visit, every

12 weeks (± 7 days) during the second year, and every 16 weeks (± 7 days) thereafter. The survival follow-up will be conducted until death or study completion, whichever is first.

The Investigator (or designee) will acquire the following information from patients who were randomized:

- Tumor assessment for all randomized patients who discontinue the trial treatment before disease progression or patients randomized but not treated. Tumor assessment will be repeated every 9 weeks (± 7 days) during the study treatment and during the first year from discontinuation of the study treatment, every 12 weeks (± 7 days) during the second year, and every 16 weeks (± 7 days) thereafter, until study completion, disease progression, death or receipt of new anti-cancer therapy, whichever is first.
- Subsequent cancer treatments (all randomized patients).
- Any SAEs considered to be related to trial treatment >90 days post last day of trial treatment, follow until resolution.
- Date and cause of death (all randomized patients).

Scans will include head and CAPs and will be sent to the central imaging vendor for archiving. If clinical progression is suspected, all relevant clinical documentation is to be submitted to the IRR for archiving and possible assessment at a later date. If clinical progression is suspected, all relevant clinical documentation is to be submitted to the central imaging vendor.

7.3 Screening

Informed consent must be obtained before any trial specific tests or evaluations are conducted.

The screening visit will occur within 21 days (unless otherwise stated) before administration of trial treatment and may be combined with baseline laboratory evaluations if both are done within 72 hours of initial dosing. Baseline scans for tumor assessment must be performed within 30 days prior to randomization. Trial eligibility will be based on fulfilling trial inclusion and exclusion criteria. The Investigator will use clinical judgment when determining the clinical significance of laboratory values at baseline and throughout the trial.

At the screening visit, information will be collected and patients will have clinical evaluations as follows:

- Informed consent
- Demographics
- Medical and Cancer history
- Physical examination (including pregnancy results, Site/Organ System Status [includes: General appearance, skin, H/E/E/N/T – Thyroid, Pulmonary, Cardiovascular, Gastrointestinal, Musculoskeletal/ Extremities, Genitourinary/Breast, Lymph Nodes, Neurological and Psychiatric]), including height and weight
- Vital signs (5-minute sitting blood pressure, pulse, respiratory rate, oxygen saturation, and oral temperature)

- ECOG performance status assessment
- Activated partial thromboplastin (aPTT) and International Normalized Ratio (INR) or Prothrombin (PT)
- Clinical laboratory tests (hematology, chemistry panel, thyroid function (TSH, T3, and T4), and urinalysis)
- 12-lead electrocardiogram (ECG)
- Pregnancy test (urine or serum) in women of childbearing potential
- Radiologic tumor assessment (within 30 days prior to randomization)
- PD-L1 expression as determined by FDA-approved PD-L1 IHC 22C3 PD-L1 assay.
- Concomitant medications
- Obtain pathology report of archival tissue.

If screening evaluations are not done within 72 hours of the initial dose of trial drug, the following evaluations will be repeated at a baseline visit:

- Physical examination (including pregnancy results, Site/Organ System Status [includes: General appearance, skin, H/E/E/N/T – Thyroid, Pulmonary, Cardiovascular, Gastrointestinal, Musculoskeletal/ Extremities, Genitourinary/Breast, Lymph Nodes, Neurological and Psychiatric]), including weight
- Vital signs (5-minute sitting blood pressure, pulse, respiratory rate, oral temperature)
- ECOG performance status assessment
- Clinical laboratory tests (hematology, chemistry panel, coagulation tests, and urinalysis)
- Non-radiologic tumor assessment (if applicable)

7.4 Clinical Visits

7.4.1 Clinic Evaluations

Once a patient is enrolled, a mandatory tumor tissue sample for biomarker research should be submitted (preferably from the same block used for PD-L1 testing).

Physical examination, vital signs, 12-lead ECG, ECOG performance status assessment, thyroid function, urinalysis, concomitant medications, and AEs will be assessed at Cycles 1, 3, 5, etc. Clinical laboratory tests (hematology, chemistry panel, and coagulation tests) will be assessed at every cycle.

- Physical examination (including pregnancy results, Site/Organ System Status [includes: General appearance, skin, H/E/E/N/T – Thyroid, Pulmonary, Cardiovascular, Gastrointestinal, Musculoskeletal/ Extremities, Genitourinary/Breast, Lymph Nodes, Neurological and Psychiatric]) including weight
- Vital signs (5-minute sitting blood pressure, pulse, respiratory rate, oxygen saturation, and oral temperature)
- 12-lead electrocardiogram (ECG)
- ECOG performance status assessment
- Clinical laboratory tests (hematology, chemistry panel, coagulation tests, thyroid function, and urinalysis)

- Concomitant medications
- Adverse Events

Note: The physical examination, weight measurement, and clinical laboratory tests may be performed up to 24 hours before dosing. Complete blood count (CBC) results must be available prior to infusion for every dose. If chemistry results are abnormal, assess again before dosing.

7.5 Tumor Assessments

- CT or MRI (if allergic to contrast media) scans will be performed every 9 weeks (± 7 days) during the study treatment and during the first year from discontinuation of the study treatment, every 12 weeks (± 7 days) during the second year, and every 16 weeks (± 7 days) thereafter to evaluate response to treatment by RECIST v.1.1.
- The same radiographic procedure (includes head, chest, abdomen, and pelvis) to define measurable lesions must be used throughout the trial for each patient.
- Patients will continue the assigned trial treatments until tumor progression (by RECIST v.1.1 criteria) by CT or MRI (if allergic to contrast media), withdrawal from the trial, or intolerance of therapy not manageable with dose modifications outlined in the protocol/package insert and/or supportive care. Note: Patients with suspected radiographic pseudoprogression, in the absence of clinical deterioration, should remain on trial treatments and be rescanned at 4 weeks or later. If progression is confirmed on follow-up scan, study treatments will be discontinued or patients on Arm 2 may be eligible for crossover. Refer to Section [7.6](#).
- Patients who discontinue trial treatments with response of CR, PR, or SD will undergo CT or MRI scan evaluations per protocol until time of PD, or death, or until study completion, or initiation of subsequent anti-cancer therapy, whichever is first.
- Patients who demonstrate clinical progression before their scans are due will have an unscheduled scan conducted to document disease status by RECIST v.1.1.
- The first scheduled tumor response assessment will be performed at 9 weeks (± 7 days), and responders (CR or PR per RECIST v1.1) will have a confirmatory scan at ≥ 4 weeks after response has been established using the same technique as baseline scans.
- All CT/MRI scans for all patients randomized on the trial will be collected prospectively and submitted to a central imaging vendor for archiving. These scans may be independently reviewed at a later time at the request of Lilly.

7.6 Pseudoprogression and Confirmation of Disease Progression

Accumulating evidence indicates a minority of patients treated with immunotherapy may derive clinical benefit despite initial evidence of PD.

Patients will be permitted to continue treatment beyond initial RECIST 1.1 defined PD if they meet the following criteria:

- Investigator-assessed clinical benefit, and do not have rapid disease progression
- Continue to meet all other study protocol eligibility criteria
- Tolerance of study drug
- Stable performance status

Treatment beyond progression will not delay an imminent intervention to prevent serious complications of disease progression (eg, CNS metastases).

A radiographic assessment/scan should be performed 4 weeks (± 7 days) after original PD to determine whether there has been a decrease in tumor size, or continued PD. The assessment of clinical benefit should be balanced by clinical judgment as to whether the patient is clinically deteriorating and unlikely to receive any benefit from continued treatment with AM0010 and/or pembrolizumab. A confirmatory scan will be required in the case of clinical deterioration suspected to be disease progression.

For patients who continue AM0010 and/or pembrolizumab beyond initial progression, confirmed progression is defined as an additional 10% increase in tumor burden volume from the time of initial PD. This includes an increase in the sum of all target lesions and/or the development of new measurable lesions. Treatment beyond confirmed progression is not allowed.

When assessing disease progression, the Investigator should use a new baseline tumor burden that includes new lesions that developed at the time of initial progression. New lesions are considered measurable at the time of initial progression if the longest diameter is at least 10 mm (except for pathological lymph nodes which must have a short axis of at least 15 mm). Any new lesion considered non-measurable at the time of initial progression may become measurable and therefore included in the tumor burden volume if the longest diameter increases to at least 10 mm (except for pathological lymph nodes which must have a short axis of at least 15 mm).

For patients in both treatment arms, global deterioration of health status (to ECOG Performance Status 2 for example) requiring discontinuation of study treatments without objective evidence of disease progression at that time should be reported as “symptomatic deterioration.” Every effort should be made to document objective progression (ie, radiographic confirmation) even after discontinuation from study treatments.

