	
 • Clinical evaluation: complete history, physical examination (Site/Organ System Status [includes: General appearance, skin, H/E/E/N/T – Thyroid, Pulmonary, Cardiovascular, Gastrointestinal, Musculoskeletal/Extremities, Genitourinary/Breast, Lymph Nodes, Neurological, and Psychiatric]), ECOG performance status, height, weight, vital signs, and documentation of concomitant medications. • Laboratory studies: hematology (WBC with differential, RBC count, reticulocyte count, and platelet count); aPTT and International Normalized Ratio (INR) or PT; comprehensive chemistry panel (sodium, potassium, chloride, CO₂, creatinine, calcium, BUN, albumin, AST, ALT, alkaline phosphatase, lactate dehydrogenase, and total bilirubin); Thyroid Function Test (TSH, free T3, and free T4); urinalysis with microscopic examination; and serum or urine pregnancy test for women of child bearing potential. • Pharmacokinetic: sparse sampling in all patients in Arm 1 and crossover and exploratory molecular biomarker sample collection in all patients. • Tumor Assessment: CT or MRI (if allergic to contrast media) scans will be performed every 9 weeks (± 7 days) during the study treatment and during the first year from discontinuation of the study treatment, every 12 weeks (± 7 days) during the second year, and every 16 weeks (± 7 days) thereafter, to evaluate response to treatment by RECIST v.1.1. • Tumor assessment will be repeated until disease progression, death, or receipt of new anti-cancer therapy, or until study completion, whichever is first, whether or not study treatment was administered • The same radiographic procedure to define measurable lesions must be used throughout the trial for each patient. • Patients will continue the assigned trial treatments until tumor progression by RECIST v.1.1 criteria (per Investigator's assessment) by CT or MRI (if allergic to contrast media), withdrawal from the trial, or intolerance of therapy not manageable with dose modifications outlined in the protocol/package insert and/or supportive care. Note: Patients with suspected radiographic pseudoprogression, in the absence of clinical deterioration, should remain on trial treatments and be rescanned at 4 weeks or later. If progression is confirmed on follow-up scan, patients in Arm 1 will be discontinued from the treatment and patients in Arm 2 may crossover to receive treatment with AM0010 with pembrolizumab if they fulfill eligibility requirements. Refer to Section 7.6. • Patients who discontinue trial treatments with response of CR, PR, or SD will undergo CT or MRI scan evaluations per protocol until time of PD or death, or until study completion or initiation of subsequent anti-cancer therapy, whichever is first. • Patients who demonstrate clinical progression will have a scan conducted at the time to document disease status by RECIST v.1.1. • The first scheduled tumor response assessment will be performed at 9 weeks (± 7 days), and responders (CR or PR per RECIST v1.1) will have a confirmatory scan at ≥ 4 weeks after response has been established using the same technique as baseline scans. • To mitigate the chance of detecting false progression (ie, pseudoprogression) early in the course of treatment with AM0010 in combination with pembrolizumab or the pembrolizumab-alone arm, patients whose scans show radiographic progression in the absence of clinical deterioration including worsening performance status as assessed by the Investigator may remain on trial treatments and an additional scan should be obtained at ≥ 4 weeks (± 7 days) as outlined in Section 7.6. If this subsequent scan shows disease progression, patients in Arm 1 will be discontinued from the treatment period of the trial; patients in Arm 2 may cross over to receive treatment with AM0010 in combination with pembrolizumab if they fulfil the necessary eligibility criteria. • All screening and on-trial CT/MRI scans for all patients randomized on the

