- Prior soft tissue radiation (eg, supraclavicular radiation, radiation of internal mammary lymph nodes, etc., as recorded on the Prior Radiation Therapy Form would preclude the selection of measurable disease in the site of radiation unless the site confirms on the Prior Radiation Therapy Form that the lesions are new since radiation was completed.

Non-Target Lesions

All of the sites of disease present at Baseline not classified as target lesions will be classified as non-target lesions. Non-target lesions must be qualitatively assessed at each subsequent time point. Examples of non-target lesions include:

- All bone lesions, irrespective of the modality used to assess them;
- Leptomeningeal disease;
- Lymphangitis of the skin or lung;
- Cystic lesions;
- Irradiated lesions that have not shown progression;
- Measurable lesions beyond the maximum number of 10;
- Groups of lesions that are small and numerous; and
- Pleural effusion/pericardial effusion/ascites.

New Lesions

Unequivocal new lesions are those that were not present at Baseline. At each time point, the presence of new lesions will be determined. New multi-focal or miliary disease of any size is considered a new lesion.

Lesions that are encountered (subsequent to the Baseline) in anatomic locations that were not scanned at Baseline will be considered new lesions and will represent progressive disease.

Lesions that were present which subsequently resolved and then recurred will be considered new lesions and will represent progressive disease.

Antitumor Response (RECIST v1.1 Guidelines)

Antitumor response will be defined as the percent of patients who achieve an objective confirmed response (complete or partial response). Disease control rate (SD for at least 16 weeks or confirmed CR or PR) also will be reported. Response will be determined according to RECIST guidelines. The original RECIST guidelines were developed and published in the Journal of the National Cancer Institute ([Therasse, Arbuck et al. 2000](#)).

Target Lesion Response (RECIST v1.1 Guidelines)

Percentage change in SLD will be evaluated by the following formulae:

1. When determining complete response or partial response:

$$(\text{Post value} - \text{Baseline value}) / \text{Baseline value} \times 100$$

2. When determining progressive disease:

$$(\text{Post value} - \text{Nadir value since treatment started}) / (\text{Nadir value since treatment started}) \times 100$$

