The following definitions will be used to evaluate response based on target lesions at each time point after Baseline:

Complete Response (CR): Disappearance of all target lesions.

Partial Response (PR): At least a 30% decrease in the SLD of target lesions, taking as reference the Baseline SLD.

Stable Disease (SD): Neither sufficient shrinkage of target lesions to qualify for PR, nor sufficient increase to qualify for PD, taking as reference the nadir SLD since the treatment started.

Progressive Disease (PD): At least a 20% increase in the SLD of target lesions, taking as reference the nadir SLD recorded since the treatment started, or, the presence of one or more new lesions. In addition to the relative increase of 20%, the sum must also demonstrate an absolute increase of at least 5 mm. The appearance of one or more new lesions is also considered progression. PET scans will not be used to determine target lesion progression or as a criterion for patient withdrawal from the study. Only CT scans or MRIs will be used for those purposes.

Not evaluable (NE): A target lesion present at Baseline which was not measured or which was unable to be evaluated leading to an inability to determine the status of that particular tumor for the time point in question. If the SLD cannot be determined at a time point and the rules for PD do not apply, a response of CR, PR, or SD cannot be assigned for that time point, and the time point response will be NE.

Not Applicable (NA): No target lesions were identified at Baseline. Patients with no target lesions identified at Baseline cannot be assessed for response. These patients will be assessed for progression only.

Not Done (ND): Scans were not performed at this time point to evaluate the target lesions.

Non-Target Lesion Response (RECIST v1.1 Guidelines)

Each non-target lesion will be qualitatively evaluated at each time point. Response of each lesion at each time point will be assessed with respect to the Baseline status. Progression will be assessed with respect to nadir size of the non-target lesions. The overall non-target lesion response for each time point will be assessed as the worst case for the non-target

lesions for that particular time point. If a non-target lesion is classified as NE/ND, the non-target response will be NE/ND unless progression is identified in the available non-target lesions. Response assessments are defined as follows:

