Complete Response (CR): Disappearance of all non-target lesions, and normalization of tumor marker level. All lymph nodes must be non-pathological in size (<10 mm short axis)
Non-CR / Non-PD: Persistence of one or more non-target lesions and or maintenance of tumor marker level above the normal limits.

Progressive Disease (PD): The “unequivocal progression” of existing non-target lesion(s) or appearance of one or more new lesion(s) is considered progressive disease.

Not Evaluable (NE): Any non-target lesion present at Baseline which was not measured or was unable to be evaluated leading to an inability to determine the status of that particular tumor for the time point in question.

Not Applicable (NA): No non-target lesions were identified at Baseline.

Not Done (ND): Scans were not performed at this time point to evaluate the non-target lesions.

Pseudoprogression: Patients whose scans show radiographic progression in the absence of clinical deterioration including worsening performance status as assessed by the Investigator may remain on study treatments and additional scan 4 weeks (± 7 days) later. If this subsequent scan shows disease progression, the patient will be discontinued from study treatments.

Response Determination (RECIST v1.1 Guidelines)

Response at each time point will be assessed as a combination of the target and non-target responses as well as the presence of new lesions according to the table below:

Time Point Response / Target and Non-Target and Best Response

Target

Time Point Response: Patients With Target (\pm Non-Target) Disease			
Target Lesions	Non-Target Lesions	New Lesions	Overall Response
CR	CR	No	CR
CR	Non-CR/non-PD	No	PR
CR	Not evaluated	No	PR
PR	Non-PD or not all evaluated	No	PR
SD	Non-PD or not all evaluated	No	SD
Not all evaluated	Non-PD	No	NE
PD	Any	Yes or No	PD
Any	PD	Yes or No	PD
Any	Any	Yes	PD

CR = complete response, PR = partial response, SD = stable disease,

PD = progressive disease, and NE = not evaluable

Non-Target

Time Point Response: Patients With Non-Target Disease Only		
Non-Target Lesions	New Lesions	Overall Response
CR	No	CR
Non-CR/non-PD	No	Non-CR/non-PD*
Not all evaluated	No	NE
Uequivocal PD	Yes or No	PD
Any	Yes	PD

CR = complete response, PD = progressive disease, and NE = not evaluable

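### After suspected pseudoprogression, Protocol 7.1 and Appendix D stop treatment on persisting RECIST progression, while Section 7.6 asks for a further 10% from a new baseline; pointers favor 7.6 but nothing gives it precedence

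*Protocol*

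**What the plan says.** All the texts below concern a patient who shows radiographic progression, is kept on treatment because pseudoprogression is suspected, and is rescanned about four weeks later or more.

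- **Protocol 7.1:** "If progression is confirmed on follow-up scan per RECIST v1.1, then discontinue study treatments". This sentence has no pointer to Section 7.6.
- **Appendix D, Pseudoprogression:** "If this subsequent scan shows disease progression, the patient will be discontinued from study treatments". There is no pointer here either.
- **Synopsis, Trial Treatment Period:** the rescan is to follow Section 7.6, and the next sentence reads "If this subsequent scan shows disease progression, patients in Arm 1 will be discontinued from the treatment period of the trial".
- **Protocol 7.6:** "confirmed progression is defined as an additional 10% increase in tumor burden volume from the time of initial PD". It adds "This includes an increase in the sum of all target lesions and/or the development of new measurable lesions", tells the investigator to take a new baseline that counts lesions which appeared at initial progression, and bars treatment after confirmed progression.

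Appendix D defines RECIST progression of target lesions as "At least a 20% increase in the SLD of target lesions, taking as reference the nadir SLD recorded since the treatment started", with an absolute rise of at least 5 mm. It adds that unequivocal progression "of existing non-target lesion(s) or appearance of one or more new lesion(s) is considered progressive disease". On new lesions it says "Unequivocal new lesions are those that were not present at Baseline".

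SAP 6.5.5.1, PFS Sensitivity Analysis 2, does not count unconfirmed pseudoprogression as an event, but does not define confirmation. SAP 6.5.4.3 defines tumor burden from target lesions only.

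**The concern.** The two rules differ in reference point (nadir and original baseline, against the scan at initial progression) and in threshold. They can therefore give opposite answers for the same rescan. Section 7.6 says that the rescan is there to separate a tumor that is getting smaller from one that continues to progress. A rule tied to the nadir and the original baseline can call the first kind progression, which defeats that purpose.

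Three things depend on the answer:

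- the mandatory treatment stop in both arms;
- whether an Arm 2 patient with suspected pseudoprogression has met the condition for crossover (Section 7.8.1 then allows at most 21 days);
- which progressions count as events in PFS Sensitivity Analysis 2.

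**Working it through.** **Inputs.** The RECIST target-lesion rule comes from Appendix D (at least 20% and at least 5 mm over nadir). The 10% rule and its new baseline come from Section 7.6. The lesion sizes are assumptions for illustration; the documents give no lesion data. Section 7.6 speaks of *tumor burden volume* but then describes a sum of target lesions, so both readings are shown. The volume reading treats lesions as spheres that change size uniformly.

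**Step 1. RECIST threshold at nadir 60 mm.** max(1.20 × 60, 60 + 5) = max(72, 65) = 72 mm.

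**Step 2. Tumor shrinking after initial progression by target growth.** Initial progression at 84 mm, rescan at 76 mm.
- Section 7.1: 76/60 = 1.267, so +26.7% and +16 mm over nadir. Still RECIST progression: stop.
- Section 7.6: threshold 1.10 × 84 = 92.4 mm; 76/84 = 0.905, so −9.5%. Not confirmed. Volume has also fallen, so the volume reading gives the same answer.

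**Step 3. New lesion that shrinks but persists.** Initial progression by a new 12 mm lesion with targets at 60 mm; rescan with targets at 56 mm and the new lesion at 10 mm.
- Section 7.1: the lesion was absent at Baseline, so it still counts as new. Still RECIST progression: stop.
- Section 7.6: new baseline 60 + 12 = 72 mm; rescan 56 + 10 = 66 mm; 66/72 = 0.917, so −8.3%. Not confirmed. Every lesion has shrunk, so the volume reading agrees.

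**Step 4. Tumor stable or slightly larger.** Initial progression by target growth at 72 mm.

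| Reading of the 10% | Section 7.6 threshold | Rescans on which the rules disagree | Rescan at 76 mm under 7.6 |
|---|---|---|---|
| Sum of diameters | 1.10 × 72 = 79.2 mm | 72 to <79.2 mm (7.2 mm wide) | 76/72 = 1.056, +5.6%: not confirmed |
| Spherical volume | 72 × 1.1^(1/3) = 72 × 1.0323 = 74.3 mm | 72 to about 74.3 mm (about 2.3 mm wide) | 1.0556³ = 1.176, +17.6%: confirmed |

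Under Section 7.1 every rescan in these windows is a stop. The size of this window depends on how *volume* is read; the conflicts in Steps 2 and 3 do not.

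**Step 5. Direction.** Where initial progression was by target growth, the sum at that scan is already at or above the RECIST threshold, so 1.1 times that sum is above it too. Any rescan confirmed under 7.6 by target growth is then also RECIST progression, and 7.1 is the stricter rule. This is not claimed for other kinds of initial progression.

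**The case against.** The best reply is that a careful reader would follow Section 7.6. It is the dedicated section, it defines confirmed progression for exactly these patients, and Section 7.1 is a general overview. The Synopsis (twice), Sections 3.0, 7.5 and 10.2.1, and SAP 6.5.2.1 all send the reader to 7.6. In the Synopsis the stop sentence directly follows such a pointer and can be read as progression from the new baseline. On the literal reading of 7.1, any new lesion that persists confirms progression, which leaves 7.6 little purpose for those patients.

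Much of this stands. A reader might infer that the documents are silent on which rule applies; they are not, and the pointers favor 7.6. But pointers are not a precedence statement, Section 7.1 names RECIST v1.1 expressly, and neither 7.1 nor Appendix D carries a pointer at its stop rule.

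The 10% is also a ceiling, not an order to continue. Section 7.6 further requires clinical benefit, tolerance and stable performance status, and Sections 6.3 and 7.1 let the physician stop treatment in the patient's interest. So the conflict is about whether continuing is permitted, not whether it is required. That narrows the point without removing it, because 7.1 makes the stop mandatory.

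A reader might also infer that 7.6 can never confirm non-target progression. Its list of what counts opens with *includes*, so it need not be exhaustive, and that stronger claim is not supported.

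**Conclusion.** The inconsistency is real and should be corrected. Sections 7.1 and 7.6 set different tests for the same rescan, and 7.1 read literally ends treatment in a patient whose disease is regressing from initial progression. The shrinking-tumor conflicts hold under either reading of *volume*. For a stable or slightly growing tumor, the disputed range in the example is between about 2.3 mm and 7.2 mm wide.

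The reach is limited. The primary ORR, the main PFS analysis and the power statement do not use the confirmation rule. The one analysis whose event set directly depends on it is a sensitivity analysis of a secondary endpoint. The number of affected patients is not given; Section 7.6 speaks only of a minority who may benefit despite initial progression. No shift in event timing can be stated, because the SAP does not say how events in PFS Sensitivity Analysis 2 are dated. A reader might infer a bias between arms, but the documents show none: the conflicting stop rules apply to both.

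**What to change.** Make Section 7.6 the single rule and say so at each place.

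1. **Protocol 7.1:** in the stop sentence, replace *per RECIST v1.1* with *as defined in Section 7.6*.
2. **Appendix D (Pseudoprogression) and Synopsis:** replace *shows disease progression* with *shows confirmed progression as defined in Section 7.6*.
3. **Protocol 7.6:** replace *tumor burden volume*, in both places, with *sum of diameters of target and new measurable lesions*.
4. **SAP 6.5.5.1, PFS Sensitivity Analysis 2:** state that confirmation means confirmed progression per Protocol Section 7.6, in both arms. The tumor burden of SAP 6.5.4.3 cannot serve here, as it leaves out new lesions.

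Optionally, Section 7.6 could add that confirmed progression also includes unequivocal worsening since initial progression of any non-target or non-measurable lesion (including new ones found at initial progression), or any further new lesion. That is a clinical choice for the sponsor and is not needed to resolve the conflict.

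The cost is small: wording changes, plus recording new-lesion diameters from scans already taken. The documents do not say whether those diameters are now captured for analysis. No extra scans or patients are needed.
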